Statistical methods:	
Phase Ia: Dose escalation is guided by a BLRM with overdose control that will be fitted to binary toxicity outcomes. The estimate of parameters will be updated as data are accumulated using the BLRM. At the end of dose escalation, the toxicity probability at each dose level will be calculated to determine an estimate of the MTD. If there are too few or no DLTs for BLRM guided dose selection, PK and/or biomarker data will be taken into consideration for RPIID determination.
 
Phase Ib: data collected during this phase will be recorded and presented in a descriptive fashion.
 
No hypothesis testing is planned in either phase.
		

Proprietary confidential information © 2023 Boehringer Ingelheim International GmbH or one or more of its affiliated companies

FLOW CHART 1: BI 1381.1 (REFMAL 473) PHASE IA (DOSE ESCALATION) TRIAL ASSESSMENTS

Flow Chart 1		Trial Treatment Days ^{a,b} Cycle = 21 Days							Post-Treatment Days ^b		
	Screening	Cycles 1, 2, and 4					Cycles 3, 5, and 6+	End-of-Treatment ^a (EOT) Visit	30-Day ^b Safety Follow-up	PFS Follow-up ^q	
Assessments	-28 to -1	1 (±2 C3+)	2 (±2 C3+)	4 (±2 C3+)	8 (±1 C1) (±2 C3+)	15 (±1 C1) (±2 C3+)	1 (±2)	(within 7 days of EOT)	(+2)		
Informed Consent ^c	X										
Inclusion/Exclusion Criteria	X										
Medical History and Demographics ^d	X										
Physical Examination ^{d, e}	X	X				X ^{e,m}	X	X	X	X	
ECOG Performance Status ^{d, e}	X	X					X (C3,5,7,9,etc)	X	X	X	
Vital Signs ^d	X	X	X	X	X	X	X	X	X	X	
12-Lead Digital Electrocardiogram ^{d, f}	X	X					X ^f	X	(X)		
Hematology and Clinical Chemistry Labs ^d	X	X			X ^m	X ^m	X		X		
Urinalysis ^d	X							X			
Pregnancy Test for Women of Child-Bearing Potential ^{d, g}	X	X					X	X		X	
Concomitant Medications	X	X	X	X	X	X	X	X	X	X	
Adverse Events	X	X	X	X	X	X	X	X	X	X	
Survival ^q										X ^q	
Blood Samples for Biomarkers [REDACTED] ^h		X	X		X		X	X			
Blood Samples for [REDACTED] ^{i, p}		X					X ^q	X	X		
Blood Samples for Pharmacokinetics ^{j, p}		X	X	X	X	X	X	X ^{j, p}	X ^j		
Biopsy ^k	(X)						(X) (end C2)	(X)			
Tumour Assessments ^{d, l}	X	Every 6 weeks (then every 9 weeks after 6 months of treatment)									
BI 754091 infusion		X					X				
DLT Assessment (report required at Phase Ia Cycle 1) ⁿ		X	X	X	X ^m	X ^m	X	X			

Flow Chart 1 Footnotes (Dose-Escalation)

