- Another biopsy (optional) should be taken upon PD (according to RECIST v1.1 and iRECIST), if possible. An optional biopsy should also be taken if a patient has stable disease over 3 subsequent disease assessment periods.

l Tumour assessments should be done according to RECIST v1.1 and iRECIST and should include CT/PET scans of the chest and abdomen and, if clinically indicated, imaging of any other known or suspected sites of disease (e.g., pelvis, brain) using an appropriate method (CT/PET scan or MRI). The same radiographic procedure must be used throughout the trial. In case of suspected (but not confirmed) bone metastasis at screening, tumour assessment at screening should include a bone scan. If bone lesions are already known or confirmed at screening, correlative imaging (X-ray or CT scan) should be performed. Correlative imaging should then be repeated at each tumour assessment (see Section 5.2.1 for more detail). Assessments will be performed by the Investigator at screening and every 2 cycles (6 weeks) for the first 6 months of treatment and once every 3 cycles (9 weeks) thereafter until PD or start of further treatment for disease, and at the discretion of the Investigator.

m Cycle 1 only

n Dose-limiting toxicities (DLTs) will be collected throughout the trial and will be assessed for dose-escalation decisions following Cycle 1. After a first cycle is completed, a BI DLT Assessment report must be sent to the Medical Monitor (see Section 4.1.5). Cycle 2 cannot begin without Safety Review Committee approval.

o If the decision is made to permanently discontinue BI 754091 during a scheduled visit, the EOT visit assessments should be performed instead of the scheduled visit assessments.

p [REDACTED] PK blood samplings are to be collected during Cycles 1 through 12, Cycle 14, Cycle 17, at the EOT visit, and the 30-day safety follow-up.

q Additional progression-free survival (PFS) follow-up visits after the 30-day safety follow-up visit will only be performed for patients who did not progress on treatment. These will be performed once every 12 weeks at least (by telephone) until PD, introduction of a new anti-cancer treatment, death, loss to follow-up, withdrawal of consent, or end of the whole trial.

Proprietary confidential information © 2023 Boehringer Ingelheim International GmbH or one or more of its affiliated companies

FLOW CHART 2: BI 1381.1 (REFMAL 473) PHASE IB (DOSE EXPANSION) TRIAL ASSESSMENTS

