6. INVESTIGATIONAL PLAN

6.1 VISIT SCHEDULE

The trial consists of 2 parts. The first part is a dose-escalation phase (Phase Ia) to determine the MTD and the recommended dose for the Phase Ib dose expansion. The schedule shown to have a more favourable safety, PK, and biomarker profile will be chosen to be further investigated in the expansion phase. The second part (Phase Ib) is an expansion phase to further evaluate safety, efficacy and PK profile of BI 754091, as well as biomarker values as a result of treatment.

Patients meeting the inclusion and exclusion criteria for the part they are participating in and who have given their written ICF, are eligible for participation in the trial. Patients will visit the clinical site at the time points specified in [Flow Chart 1](#) (dose escalation) and [Flow Chart 2](#) (dose expansion). If a patient misses a scheduled visit, and reports to the Investigator between the missed visit and the next scheduled visit, the assessments for the missed visit must be done with the actual date and the reason must be given for the delayed visit. For the biopsies and PK sampling procedures of Cycle 1, the patient must however still be under treatment and not in a treatment break period in order to perform the evaluations planned for the missed visit. The next visit must then take place at the scheduled time after the first administration of the trial drug in the respective treatment cycle.

Once the decision for any reason is made for a patient to stop the treatment with BI 754091, an EOT visit must occur as soon as possible (preferably within 7 days). After the EOT visit, the patient must undergo a follow-up evaluation 30 (+2) days after the last BI 754091 administration.

The trial will be conducted according to the principles of Good Clinical Practice (GCP).

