6.2.3 Follow-up period and trial completion

6.2.3.1 End-of-treatment visit

The EOT visit will be performed after permanent discontinuation of trial medication for any reason, as soon as possible, but no later than 7 days after permanent discontinuation of the trial medication or when the Investigator decided with the patient to permanently discontinue the trial medication or became aware that the trial medication had been terminated.

The assessments of the EOT visit will then be performed instead of at the next planned visit. If the patient finishes active treatment without having PD, tumour assessment/imaging must be performed at the time of treatment discontinuation, unless it has been done within the past 4 weeks.

For patients still on treatment with ezabenlimab at the time point of this protocol amendment, the investigators are asked to prepare for discontinuation of patients from the current investigational treatment with ezabenlimab and to switch them to alternative available treatment options outside of the current protocol no later than by the final availability of ezabenlimab in August 2023 the latest. After this date treatment with the ezabenlimab will no longer be available.

For these patients only EOT visit will be performed. 30-day post-treatment safety visit as well as Progression-free survival visits are not applicable.

6.2.3.2 30-day post-treatment safety visit

The safety follow-up visit is performed 30 (+2) days after permanent discontinuation of the trial medication. The information collected at this visit must include all new AEs that occurred after the EOT visit, and a follow-up of AEs ongoing at EOT.

A patient will be considered as having completed the trial if he/she discontinues because of PD and has performed the safety follow-up visit 30 days after EOT, or was lost to follow up, or withdrew consent for further evaluation at the EOT visit. If the patient discontinues for any other reason, he/she will be considered as withdrawn.

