7.3.4 Safety analyses

Adverse events will be coded using the Medical Dictionary for Regulatory Activities (MedDRA) coding dictionary. Standard BI summary tables and listings will be produced. Statistical analysis and reporting of AEs will concentrate on treatment-emergent AEs. All AEs with an onset between start of treatment and end of the REP, a period of 30 days after the last dose of trial medication, will be considered 'treatment-emergent' and assigned to the treatment period for evaluation. Adverse events that start before first drug intake and deteriorate under treatment will also be considered as 'treatment-emergent'.

All treated patients will be included in the safety analysis. In general, safety analyses will be descriptive in nature and will be based on BI standards. No hypothesis testing is planned.

Frequency, severity, and causal relationship of AEs will be tabulated by system organ class and preferred term after coding according to the current version of MedDRA.

Laboratory data will be analysed quantitatively as well as qualitatively. The latter will be done via comparison of laboratory data to their reference ranges. Values outside the reference range as well as values defined as clinically relevant will be highlighted in the listings.

Treatment groups will be compared descriptively with regard to distribution parameters as well as frequency and percentage of patients with abnormal values or clinically relevant abnormal values.

Vital signs, physical examinations, or other safety-relevant data observed at screening, baseline, during the course of the trial and at the end-of-trial evaluation will be assessed with regard to possible changes compared to findings before start of treatment.

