## **6. GENERAL ANALYSIS DEFINITIONS**

### **6.1 TREATMENT(S)**

In this Phase I trial, treatments are not randomized. Different dose levels of BI 754091 will arise in phase Ia and there is only one dose level in the 4 cohorts of phase Ib. Data of phase Ia and phase Ib will be displayed separately. In addition, for both phase Ia and phase Ib, data will be presented for all cohorts separately.

For phase Ia, the initial trial medication (i.e. dose level) assigned at the beginning of the first treatment cycle will be used as label of the analysing treatment.

Table 6.1: 1 Definition of analysing treatment periods for safety analysis

Analysing Treatment Period	Start Date	Stop Date
Screening	Date of informed consent	Date/Time of the first administration of trial treatment
On-treatment	Date/Time of the first administration of trial treatment	Date of the last administration of trial treatment + 30 days (residual effect period)
Follow-up	Date of the last administration of trial treatment + 31 days	Date of the last per protocol visit

Note: a 30-day residual effect period (REP) is defined for this trial.

For safety analyses, AEs will be classified to one of the following time periods: “Screening”, “On-Treatment” or “Follow-up.” This will be applied for all adverse events. Detailed rule for assigning AEs to these time periods are listed below:

- If the date of informed consent  $\leq$  AE onset date  $<$  date/time of first administration of BI 754091, then the AE is assigned to “Screening”;
- If date/time of first administration of BI 754091  $\leq$  AE onset date  $\leq$  date of last administration of BI 754091 + 30 days, then the AE is assigned to “On-Treatment”;
- If AE onset date  $>$  date of last administration of BI 754091 + 30 days, then the AE is assigned to “Follow-up”

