## **7.8.2      Laboratory data**

The analysis of laboratory data will be descriptive in nature and will be based on BI standards. The same on-treatment period as considered for the analysis of adverse events will be applied for laboratory values. Patients having at least one post-baseline laboratory value will be displayed in the descriptive analyses. Patients with missing CTCAE grade at baseline or no baseline value but with post-baseline values will be displayed in a new category “missing CTCAE grade at baseline” for those laboratory parameters where CTCAE grading is applicable. CTCAE grades for applicable laboratory parameters will be calculated according to CTCAE Version 5.0.

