### **7.8.2.1      Analysis**

The Laboratory tests will be classified into the following categories:

- Primary- full analysis
- Secondary- listing of possible clinically significant values
- Diagnostic- listing of all observed values
- Not analysed

The following outputs will be presented for primary laboratory tests:

- Descriptive statistics, including changes from baseline
- Frequency of patients with shifts from baseline
  - Shifts will be defined in terms of
    - CTCAE grades will be used for laboratory tests with CTCAE grades defined
    - The upper and lower reference limits will be used for laboratory tests without CTCAE grades
- Frequency of patients with possible clinically significant abnormalities (definitions see [Section 7.8.2.2](#))

The analysis of secondary laboratory tests will be limited to tabulation of the frequency of patients with possible clinically significant abnormalities (definitions see [Section 7.8.2.2](#)).

Laboratory tests classified as “diagnostic” are recorded as a follow-up to abnormalities of associated lab tests for diagnostic purposes i.e. amylase and lipase would be measured to investigate possible pancreatitis. These values will be presented in a separate listing. No other analyses will be performed

Analyses of descriptive statistics should use normalized lab values and will be displayed by calculated visit instead of actual visit reported to ensure a common handling of all laboratory assessments and to account for unscheduled visits representing a repeated laboratory measurement (see [Table 6.7: 2](#) and [Table 6.7: 3](#)).

Analyses of frequencies of patients with potential clinical significance, analyses of shift, and liver function categories tables should use converted values.

Baseline for safety laboratory parameters will be the last available measurement before the start of study drug. Laboratory measurements taken up to 30 days after the last administration of study drug will be considered as on-treatment.

Primary laboratory test results will be presented in CTR section 15.

Secondary laboratory test results will be included in Appendix 16.1.13.1.

Diagnostic laboratory test results will be listed in Appendix 16.1.13.1.

Laboratory test that are not analysed will be listed in Appendix 16.2.8.

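### Laboratory samples from an on-time safety visit on Day +31 or later are classed as follow-up by the SAP's 30-day cut-off and drop out of the on-treatment tables

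*SAP*

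**What the plan says.** - **Laboratory cut-off.** SAP 7.8.2.1: "Laboratory measurements taken up to 30 days after the last administration of study drug will be considered as on-treatment". SAP 7.8.2 ties this to the adverse-event rule: "The same on-treatment period as considered for the analysis of adverse events will be applied for laboratory values". SAP Table 6.1: 1 starts follow-up at "Date of the last administration of trial treatment + 31 days". The length is that of the protocol's residual-effect period, "a period of 30 days after the last dose of trial medication" (Protocol 7.3.4).
- **Safety visit.** Protocol 6.1: "the patient must undergo a follow-up evaluation 30 (+2) days after the last BI 754091 administration". Protocol 6.2.3.2 uses another anchor: "The safety follow-up visit is performed 30 (+2) days after permanent discontinuation of the trial medication".
- **Phase Ia laboratory schedule.** In Flow Chart 1 the row "Hematology and Clinical Chemistry Labs" is marked at screening, on Day 1 of each cycle, on Days 8 and 15 of Cycle 1 only, and at the 30-day visit. The end-of-treatment (EOT) cell is empty. Under footnote o, if permanent discontinuation is decided at a scheduled visit, "the EOT visit assessments should be performed instead of the scheduled visit assessments".
- **Phase Ib laboratory schedule.** In Flow Chart 2, in the text available for review, the row is marked at screening, on Day 1 of Cycles 1 to 9, on Day 1 of Cycles 12, 15, 18 and so on, and in the PFS/OS follow-up column. The EOT and 30-day cells are empty.
- **Use of the window.** The footnotes to SAP Table 7.8.2.2: 1 define the shift tables as baseline against on-treatment. The other laboratory tables take their period from SAP 7.8.2.

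**The concern.** The visit tolerance runs in one direction only. The first permitted day is the last day of the laboratory window, and every other permitted day falls after it. A site that keeps exactly to the schedule can thus produce a sample that the on-treatment tables discard.

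This matters because that sample may be the only scheduled look at laboratory values after the final dose. Protocol 2.3 describes immune-related liver effects as often being transaminase rises without symptoms. Under Protocol 5.3.6.8.1 a laboratory change becomes an adverse event only if the investigator judges it clinically relevant, so the adverse-event tables need not pick up what the laboratory tables lose. SAP 7.8.1 already recognises that 30 days can be too short for immune-related events and adds tables for later onsets. No counterpart is stated for laboratory data.

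**Working it through.** The plan gives no figure of its own on this point, so the check sets permitted visit days against the cut-off.

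**1. Anchor at last administration (Protocol 6.1).** Permitted days are {30, 31, 32}. A value is on-treatment if its day is ≤ 30. Day +30 is kept; Days +31 and +32 are follow-up. So 1 of 3 permitted days is kept and 2 of 3 are lost.

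**2. Anchor at permanent discontinuation (Protocol 6.2.3.2).** Let L be the number of days from last infusion to discontinuation. The documents give no distribution for L, so it is an assumption. Dose delays of up to 6 weeks are allowed (Protocol 4.1.4), so L above zero is realistic. Permitted days are {L+30, L+31, L+32}.

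| L | Permitted days | Kept, cut-off +30 | Kept, cut-off +32 |
|---|---|---|---|
| 0 | 30–32 | 1 of 3 | 3 of 3 |
| 1 | 31–33 | 0 | 2 of 3 |
| 2 | 32–34 | 0 | 1 of 3 |
| 3 | 33–35 | 0 | 0 |
| 21 | 51–53 | 0 | 0 |

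Moving the cut-off to +32 therefore repairs the problem fully only if the anchor is the last administration.

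**3. Is there a substitute sample in Phase Ia?** From Cycle 2 on, Flow Chart 1 marks laboratory tests only on Day 1 of a cycle and at the 30-day visit. If treatment stops at what would have been the next Day 1, footnote o replaces that visit with the EOT set, which has no haematology or chemistry mark. For a patient whose last infusion is in Cycle 2 or later, the 30-day draw is the only scheduled sample after it. A patient who stops after the first infusion also has the Cycle 1 Day 8 and Day 15 samples, both inside the window.

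**4. Phase Ib.** There are two readings of Flow Chart 2. If the last laboratory mark belongs under the 30-day visit, the Phase Ia mismatch carries over. If the row is as it appears, no 30-day sample is scheduled and this rule has nothing to discard. Footnote o of that chart says the PFS/OS contacts may be by telephone, which makes a blood draw there unlikely and a displaced mark plausible. The available text cannot settle it.

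**5. By-visit descriptive tables.** With no delays and a last infusion on Cycle k Day 1, the study day of the visit is 1 + 21(k − 1) + d. For k = 2:
- d = 30 gives Day 52 and d = 31 gives Day 53, both in the Cycle 3 window (33–53).
- d = 32 gives Day 54, in the Cycle 4 window (54–74).

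The windows in SAP Tables 6.7: 2 and 6.7: 3 would accept these days. Whether the values are first removed as follow-up depends on how SAP 7.8.2 is applied. Neither table has an EOT or follow-up slot.

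**The case against.** The strongest reply is that the cut-off is deliberate. It is the trial's 30-day residual-effect period, used consistently in both documents and applied on purpose to laboratory values as well as adverse events. That is correct, and it is a good reason to leave the adverse-event rule alone. It does not explain why a sample the protocol asks for, taken on a day the protocol permits, should leave the safety tables.

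Several limits on the effect do stand:
- Samples on Day +30, and unscheduled samples up to Day +30, are kept because the window is defined by date. Patients with laboratory toxicity are likely to have such samples; Protocol 10.2, for instance, asks for more frequent liver tests after Grade 2 hepatic events.
- The potential Hy's Law listing in SAP 7.8.2.1 has no on-treatment limit.
- The Phase Ib secondary laboratory endpoint counts abnormalities reported as adverse events (SAP 5.2.2.2), not these tables.
- Patients still on treatment at the last amendment have only the EOT visit (Protocol 6.2.3.1).

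A reader might infer that the 30-day visit supplies the only post-infusion laboratory data throughout the trial. The flow charts support that only for Phase Ia patients treated beyond Cycle 1. A reader might also derive a rate: 40% of visits if clinics run on weekdays and infusions are spread evenly over the week, or 67% if the three permitted days are equally likely. Neither assumption is in the documents, and both figures would count visit dates, not missed toxicities.

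**Conclusion.** The mismatch is in the text and needs no assumption: laboratory values from a compliant safety visit on Day +31 or later are classed as follow-up. They leave the shift tables explicitly, and the other on-treatment abnormality tables through SAP 7.8.2. With the last-administration anchor, 2 of 3 permitted days are affected; with the discontinuation anchor and any lag of 1 day or more, all are.

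The firm scope is Phase Ia, about 15 of about 145 patients, and within it those whose last infusion is in Cycle 2 or later. For the roughly 130 Phase Ib patients the conclusion depends on what the Flow Chart 2 row is meant to say. The number of patients who lose a value cannot be computed, because no distribution of visit days or of L is given. The documents also do not show that laboratory toxicity would in fact be under-counted. They show that the rule can discard the one scheduled sample that might reveal it. This is a modest defect that is cheap to remove.

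**What to change.** 1. In SAP 6.1, 7.8.2 and 7.8.2.1, state that laboratory assessments from the 30-day safety follow-up visit count as on-treatment by nominal visit, whatever the calendar day. A bare +32 cut-off is not enough: with the discontinuation anchor it misses every permitted day once L is 3 or more.
2. Say where these results go in the by-visit tables, since SAP Tables 6.7: 2 and 6.7: 3 have no follow-up slot.
3. Keep the 30-day residual-effect period for adverse-event onset.
4. Reconcile the visit anchors in Protocol 6.1 and 6.2.3.2, and clarify the laboratory row of Flow Chart 2.

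**Cost.** A short SAP edit and a programming rule keyed to the visit label. The laboratory period will differ slightly from the adverse-event period, which needs a footnote. With the last-administration anchor it gains at most 2 days (32 − 30). With the discontinuation anchor it gains up to L + 2 days, which is a reason to settle the anchor first.
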